#### Title

Evaluation of text messaging as an educational method to improve healthcare utilization

#### 1. Background

Page numbers from a sponsor's protocol/grant may be referenced in 1a and 1b.

 a) Provide an introduction and background information. Describe past experimental and/or clinical findings leading to the formulation of the study, if applicable. Investigator Initiated studies must cite references in the response provided or attach a bibliography. \*?HELP?\*

Health care utilization is a issue germane to health care providers, insurers, and patients alike. Reducing non-urgent visits to the emergency department (ED) and primary care providers can improve both the quality and cost of care. There are barriers, however, to educating patients about more appropriate health care utilization. Low health literacy is one such barrier, particularly for caregivers of pediatric patients. Research reveals that up to half of caregivers seeking treatment at the ED have low levels of health literacy; levels that can make it more difficult to not only make sound decisions, but also provide effective follow-up care. Moreover, low levels of literacy perpetuate a cycle of seeking care for non-urgent conditions. Education initiatives designed to counteract the effects of low health literacy on health care utilization have been shown to reduce non-urgent ED visits by as much as 80%. These education interventions, while effective, are complex, costly, or time-intensive. For example, home visits by a nurse, parenting classes, and video tools are all shown to reduce non-urgent ED use, but each poses a unique problem for implementation in high volume, urban, pediatric primary care clinic. To date, no study has examined the effectiveness of text messaging as a possible avenue for educating caregivers about issues related to health care utilization. Text messaging has been shown to support behavioral change, and represents a fast and cost-effective alternative to more labor-intensive and expensive alternatives.

Danis Pediatrics, the pediatric practice of Saint Louis University physicians within SSM Cardinal Glennon Children's Medical Center (CGCMC), serves as a medical home to primarily urban, low-income patients. In the first half of 2014 alone, there were 5259 visits to the ED by caregivers of patients < 13 months of age. Of those, 520 Danis Pediatrics patients accounted for 919 of those visits. In short, just under 1 in 5 visits to the CGCMC ED is a Danis patient, and Danis patients visit the ED approximately 2 times in the first year. Previous studies of patients at Danis Pediatrics suggest that this population has access to text messaging and is interested in receiving healthcare-related information from their pediatric provider.

b) Describe any animal experimentation and findings leading to the formulation of the study, if there is no supporting human data.

NA

## 2. Purpose of the study

a) Provide a brief lay summary of the project in <200 words. The lay summary should be readily understandable to the general public.

Our overall goal is to assess the feasibility and effectiveness of using text messages as an educational tool in order to improve health care utilization among the parents and caregivers of newborns; in particular, we seek to understand how educational text messages counteract the effects of low health literacy as it relates to non-urgent visits to the emergency department.

Page numbers from a sponsor's protocol/grant may be referenced in 2b and 2c.

b) List your research objectives (specific aims & hypotheses of the study).

## Research Objectives

- 1) Evaluate the feasibility of sending educational text messages to the caregivers of newborns through 6 months of age.
- 2) Assess how text messaging affects urgent and non-urgent health care utilization across caregivers with varying levels of health literacy.

## Hypotheses

- 1) Text messaging is a feasible and welcomed educational tool for caregivers of newborns.
- 2) Receiving educational text messages reduces the number of non-urgent visits to the ED for caregivers across all levels of health literacy.
- c) Describe the study design (e.g., single/double blind, parallel, crossover, control, experimental, observational, etc.). If the study is investigator-initiated, a timeline for individual subject recruitment, follow-up, and analysis for the study is required. Also, indicate if the subjects will be randomized.

We propose a prospective, randomized, single-blind experiment assessing the effectiveness of receiving educational text messages on health care utilization at caregivers of newborns across varying levels of health literacy.

All caregivers of newborns less than 2 months of age will be approached for enrollment during regular clinic visits to Danis Pediatrics in Cardinal Glennon Children's Medical Center. Enrollment will take place following their visit with a provider; we anticipate this process will take no more than 15 minutes. Subjects will receive educational text messages four times per week until the child is 6 months of age. The research team will conduct a review of the child's medical records until the child is one year old. We will enroll up to 260 participants, and we anticipate the study continuing for an additional 18 months - including time for analysis - beyond the date when the final subject is enrolled.

d) If subjects will be given placebo, please justify placebo use. \*Error! Hyperlink reference not valid.\*

#### 3. Study Procedures

a) Yes No

No

Is this project a multicenter study (i.e., same project is conducted elsewhere by a different investigator) OR does this study involve conduct of research at multiple sites?

Is SLU acting as a coordinating center for other sites OR is the SLU PI a direct recipient of a federal grant for this research? If yes, complete and attach the Supplemental Application for Coordinating Center Activities.

Yes No

Will the SLU site be participating in all parts/procedures/arms of the study?

If No, explain what SLU will NOT participate in:

Page numbers from a sponsor's protocol/grant may be referenced in 3b, 3c, and 3d.

b) Describe all the procedures, from screening through end-of-study, that the human subject must undergo in the research project, including study visits, drug treatments, randomization and the procedures that are part of standard of care. Specify which procedures are for research and which are standard of care. Please note: The box below is for text only. If you would like to add tables, charts, etc., attach those files in the Attachment section (#16).

Any caregiver of a newborn, aged 0-2 months, that receives primary care at Danis Pediatrics, has reliable cellular and text messaging service, and speaks English will be approached for enrollment. If the caregiver is interested in receiving educational text messages about their new baby, they will meet with a member of the research team.

At enrollment, caregivers will complete a brief demographic survey and be given a researcher-administered health literacy test. We anticipate enrollment will take no longer than 15 minutes. Following enrollment, participants will be randomly assigned to either the group that receives only enhanced standard of care documents, or receives text messages in addition to enhanced standard of care documents.

As a part of the regular standard of care at Danis Pediatrics, at all routine well-child exams, caregivers receive anticipatory guidance, as well as information related to their child's growth and development in the form of Bright Futures handouts. Bright Futures is a series of informative, age-specific, handouts produced by the American Academy of Pediatrics (AAP) for use by providers as a tool to educate patients on growth, development, and safety. All subjects will receive a condensed version of the Bright Futures content at their scheduled 1, 2, 4, and 6 month well child exams. This enhanced standard of care document (ESoC) is designed to be more readable, digestible, and more directly address the most common causes of non-urgent ED visits, than the Bright Futures handouts received as a part of the regular discharge process at Danis Pediatrics.

Following enrollment and assignment into one of the two experimental groups, subjects assigned to the text messaging intervention group will receive four educational messages per week until their child is 6 months of age. Subjects will receive no more than 104 messages during the study period. The text messages directly reflect the Bright Futures and ESoC content, addressing infant development, safety, care, and the most

common causes of non-urgent visits in the first year. Again, all participants will receive ESoC documents from the research team at scheduled 1, 2, 4, and 6 month well child exams.

Upon completion of text messaging and distribution of ESoC handouts, the research team will review the child's electronic medical record, documenting the volume and type of health care utilization until the child is one year old. The research team will type and count visits to the emergency department and Danis Pediatrics, as well as call volume.

c) If the proposed study is a clinical trial where a drug, vaccine, device or other treatment is compared to a placebo group or comparison treatment group, what are the guidelines or endpoints by which early decisions regarding efficacy or lack of efficacy can be made? For example, it may be reasonable to stop enrollment on a study when efficacy has already been clearly demonstrated, to avoid unnecessary enrollments of additional subjects. Alternatively, it may be reasonable to stop enrollment when it is clear that efficacy will never be demonstrated, given the statistical power of the study as designed. Describe the guidelines that are in place to assist in making these determinations, if relevant to the proposed study.

NA

d) Describe how data analysis will be performed (statistical tests, methods of evaluating data) and indicate the smallest group/unit for which separate reporting will occur. For studies involving a questionnaire, if data and reliability information are available, please describe or provide references. For full board, unfunded studies describe sample size determination and power analysis. If none, please justify.

The sample size for the study was estimated to achieve 80% statistical power, assuming a non-directional test and a critical level for significance of alpha = .05, based on the primary outcome variable of emergency department (ED) use. The study was powered on the latter variable because it is expected to yield the smallest intervention effect. Danis Pediatric Center patients <13 months of age have a six-month incidence rate of presentation at the Cardinal Glennon Children's Hospital ED of 41% (clinic data). This rate was assumed as the baserate behavior for the Control group in the proposed research. Assuming an incidence rate in the Intervention group of 20-25% (difference from baserate behavior of 16-21%), sample sizes ranging from 84-147/group would yield adequate statistical power. Because this is a first-time study of this intervention in relation to ED use, a 23% effect size was targeted, requiring 115 subjects/group or 230 subjects total. Danis Pediatric Center encounters with study eligible patients average ~25 patients/week (conservative estimate); thus, with a 67% response rate (consistent with other research of this type in the Department of Pediatrics), the study will require 12-14 weeks to enroll this target number.

The primary outcome of 6-month ED use (no vs. yes) will be compared between study groups, Intervention vs. Control, using the chi-squared test of association. Other categorical outcome variables (e.g., keeping well child appointments, keeping immunization appointments) will also be analyzed this way. Multivariate analyses of dichotomous outcomes, including multiple logistic regression, will be conducted with Group as the independent variable and covariates like patient age, race, gender, etc., included as control variables. Time-to-event data (e.g., time to first ED visit after study entry) may be evaluated using a Cox proportional hazards regression model with Kaplan-Meier curves.

Because this study rests on the assumption that text messages are both delivered and read, this study has several validity checks in place. First, to assure messages are delivered, the company (TeleVox) that will service text messaging for this study provides daily reports regarding

message status. That is, we can see - within 24 hours - whether or not a message has been successfully sent to a subject. In this regard, we can then address any message failures with subjects by phone, or at subsequent visits. While we can track whether or not a message has been received, knowing if a message has been read or understood is a more difficult. We've included questions on our post-test that inquire about message use and subject involvement. These questions will serve as a statistical covariates in the analysis, such that the treatment effect would be stratified by the levels of self-reported use of and involvement with the texts.

- 8. Subject Population In the space below, please detail the participants that you are requesting to recruit (include description of each group requested)
- a) Expected age range of subjects. (For example ≥ 18 yrs to 90 yrs).

Subjects are likely between 15 and 65 years of age (age of caretakers including parents and guardians).

b) Number of evaluable subjects to be accrued at SLU or SLU site (this includes all sites under the direction of the SLU PI). up to 260

Exceeding the number listed here is a protocol violation. Prior IRB approval is required if additional participants are to be accrued. If applicable, this number should be consistent with your power analysis described in 3d.

c) Number of evaluable subjects to be accrued study wide. \*?HELP?\*

d) If applicable, state the rationale for involvement of potentially vulnerable subjects to be entered into the study, including minors, pregnant women, economically and educationally disadvantaged, or decisionally impaired individuals. Specify the measures being taken to minimize the risks and the chance of harm to the potentially vulnerable subjects.

In this study, for those participants less than 18 years of age, though minors, they will have given birth and are therefore considered emancipated minors who may consent for themselves.

Because of clinic demographics, this study may involve subjects who are economically and educationally disadvantaged with low levels of health literacy. The research team will take special care to engage in culturally competent communication with subjects. In particular, all team members will be trained in the neutral administration of the health literacy test.

e) If women, minorities, or minors are not included, a clear compelling rationale must be provided unless not applicable. Examples for not including minors: disease does not occur in children; drug or device would interfere with normal growth and development; etc. If federally funded reference appropriate section of the sponsors protocol/grant. \*?HELP?\*

	Participation is limited to English-speaking parents and/or guardians because of cost and communication barriers.
f)	If any specifically targeted subjects are students, employees, or laboratory personnel, specify the measures being taken to minimize the risks and the chance of harm to these potentially vulnerable subjects.
g)	Describe how potential subjects will be identified for recruitment (e.g., chart review, referral from individual's treating physician, those individuals answering an ad). How will potential participants learn about the research, and how will they be recruited (e.g., flyer, e-mail, web posting, telephone, etc.)? Upload recruitment materials in the Attachment Section (#16). Important to remember: potential subjects cannot be contacted before IRB approval. NOTE: The use of SLU owned websites in an approved SLU format (e.g., Cancer Center website, etc.) are always approved methods of recruitment.
	Parents and/or guardians of all newborns between 0 and 2 months of age will be recruited at scheduled visits to Danis Pediatrics in Cardinal Glennon Children's Medical Center. Subjects will be identified by their child's pediatric provider, including nurses. In addition, flyers will be placed in exam rooms so that caregivers may inquire about participation. No additional recruitment of subjects will be required beyond serving those already part of the medical home.
8.	Subject Population (continued)
Pa	ge numbers from a sponsor's protocol/grant may be referenced in 8h.
h)	Inclusion and Exclusion Criteria.
	Identify inclusion criteria.
	All English-speaking parents and/or guardians of newborns, aged 0 to 2 months, who receive primary care at Danis Pediatrics will be considered for participation. In addition, they must have reliable mobile phone service and be able to receive text messages.

Identify		

Non-English speaking caregivers and those without reliable text messaging service will be excluded from this study.

i) Compensation. Explain the amount and schedule of compensation, if any, that will be paid for participation in the study. Include provisions for prorating payment.

Subjects will not be compensated for participation.

j) Describe who will cover study related costs. Explain any costs that will be charged to the subject.

The cost of receiving the text messages will be the responsibility of the participant, which will be explained prior to enrollment. This generally amounts to no more than ten cents per message, but many individuals have a specific number of text messages per month that are included in their plan. The cost of messages being sent to participants, will be covered by Danis Pediatrics.

All medical care costs related to the care of the child will be covered by the child's caregiver and their insurance. No additional visits to Danis Pediatrics will be required for this study beyond what is recommended as a part of the newborn standard of care at Danis Pediatrics.

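### Does the 41% control rate, taken from clinic data, undermine the stated 80% power when controls also receive the ESoC document?

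*Protocol*

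**What the plan says.** Protocol section 3d bases the sample size on the yes/no outcome of six-month ED use, with 80% power and a two-sided alpha of 0.05. The control figure is a six-month incidence in clinic patients under 13 months of age, at the "Hospital ED of 41% (clinic data"), and it is carried over as it stands: "This rate was assumed as the baserate behavior for the Control group in the proposed research". The effect is introduced as "Assuming an incidence rate in the Intervention group of 20-25% (difference from baserate behavior of 16-21" percent), which gives 84 to 147 per group. The planning point is then fixed: "a 23% effect size was targeted, requiring 115 subjects/group or 230 subjects total".

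Section 3b describes the arms. Subjects are "randomly assigned to either the group that receives only enhanced standard of care documents" or to text messages on top of those documents. It adds that "all participants will receive ESoC documents from the research team" at the 1, 2, 4 and 6 month well child exams. ESoC is a condensed form of the Bright Futures content, designed to "more directly address the most common causes of non-urgent ED visits, than the Bright Futures handouts". Families at the clinic ordinarily get those older handouts when they leave a visit.

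Sections 2c and 8b allow enrolment of up to 260. Section 3d names the chi-squared test for the primary outcome.

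**The concern.** The clinic patients behind the 41% presumably had the regular Bright Futures handouts, since section 3b presents those as usual care and ESoC as something the research team supplies. Trial controls get more than that, and the addition is aimed at ED visits. Section 1a also says that education programmes have cut non-urgent ED visits substantially. It therefore seems inconsistent to expect the content to work by text message while assuming that the same content on a better handout leaves the control rate at 41%.

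If ESoC did lower ED use in controls, less room would be left for the texts to show a benefit, and true power could be below 80%. Section 3d varies only the intervention rate. It does not say whether a rate, a ratio or a difference would persist at another control rate. At stake is how much weight a null result could bear.

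**Working it through.** **Inputs (section 3d).** Control rate p1 = 0.41; intervention rate p2 = 0.20 to 0.25; 115 per group at the planning point; power 0.80 (z = 0.8416); two-sided alpha 0.05 (z = 1.960). Equal allocation is implied by the equal group sizes.

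**Step 1: reproduce the stated sizes.** With p̄ = (p1 + p2)/2 and d = p1 − p2:

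n0 = [1.960·√(2p̄(1−p̄)) + 0.8416·√(p1(1−p1) + p2(1−p2))]² / d²

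n = (n0/4)·[1 + √(1 + 4/(n0·d))]² (continuity correction)

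| p1 vs p2 | n0 | n corrected | stated |
|---|---|---|---|
| 41% vs 20% | 74.3 | 83.5 | 84 |
| 41% vs 23% | 104.2 | 115.1 | 115 |
| 41% vs 25% | 134.4 | 146.6 | 147 |

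All three figures are recovered. The 23% in the protocol must be the intervention rate, so the planned difference is 41 − 23 = 18 points. A 23-point difference (41% vs 18%) would need only 69 per group.

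**Step 2: power at 115 per group.** Power = Φ[(d − 1/n − 1.960·√(2p̄(1−p̄)/n)) / √((p1(1−p1) + p2(1−p2))/n)]; the uncorrected version drops 1/n. For 41% vs 23%: (0.1713 − 1.960 × 0.0615)/0.0604 ≈ 0.84, so power is 80%. Uncorrected, it is 84%.

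**Step 3: lower control rates.** The protocol gives no ED rate under ESoC, so 38% and 35% are assumptions. Three readings of the effect are possible: keep the 23% rate, keep the relative risk 23/41 = 0.561, or keep the 18 points. Power is corrected, with uncorrected in brackets:

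| Control rate | 23% kept | Relative risk kept | 18 points kept |
|---|---|---|---|
| 41% | 80% (84%) | 80% (84%) | 80% (84%) |
| 38% | 65% (70%) | 75% (80%) | 82% (86%) |
| 35% | 46% (52%) | 70% (75%) | 85% (88%) |

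The intervention rates in the relative-risk column are 0.38 × 0.561 = 21.3% and 0.35 × 0.561 = 19.6%. In the last column they are 20% and 17%.

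**Step 4: the enrolment cap.** 260 enrolled means 130 per group, assuming equal allocation and no loss. With the relative risk kept, power is 81% (84%) at a control rate of 38% and 76% (80%) at 35%. With 23% kept, it is 71% (75%) and 51% (57%).

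**Reading.** The two ways in which section 3d gives the effect are one statement at the planned control rate: 41 − 25 = 16 and 41 − 20 = 21. They separate only when another control rate is put in. The first column of step 3 is the harshest because it lets ESoC lower ED use in controls while leaving the intervention arm, which gets the same document, at 23%.

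**The case for a change.** The strongest case for a change is this. The texts carry the ESoC content, so their effect may overlap with ESoC's rather than add to it. In that case the 18-point column is the least plausible and the 23% column deserves weight. A fall of only 3 points in controls then takes power to 65%, and the room up to 260 does not restore it. With controls at 35%, 80% power at 115 per group needs an intervention rate of at most 17.9% (18.7% uncorrected), below the 20-25% that section 3d expects. A sentence and a short table would cost nothing.

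What stands is that the protocol gives no reason for applying the clinic rate to controls on ESoC, and that power is sensitive to this input. What does not stand is that 80% depends on ESoC having no effect: with the 18-point difference kept, power is 82% to 85%. Nor is a fall of 3 or 6 points supported by anything in the protocol. ESoC is aimed at non-urgent visits, whereas the powered outcome is any ED use, so an effect on the 41% could be diluted. The chi-squared test is named without a continuity correction, and the uncorrected power at the planning point is 84%, which leaves some slack.

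**Conclusion.** No change is needed. The stated sizes reproduce, and the 80% is correct for 41% against 23%. Section 3d introduces both rates as assumptions, and section 3b makes clear that the contrast is texts plus ESoC against ESoC alone. Taking a control rate from local records is ordinary practice. Whether it applies under ESoC is a fair question, but the protocol holds nothing that would answer it.

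The possible size runs from 46% to 85% corrected power at an assumed 35% control rate, and from 65% to 82% at 38%, depending on which effect measure persists. That range has no established direction, so it shows no shortfall. A sensitivity table would alter neither the sample size, the arms nor the test. A null result would be read from the observed difference and its confidence interval, which do not depend on the planning rate. Because both arms receive ESoC, the comparison remains unbiased at any control rate. A line saying why 41% is expected under ESoC, or power over a few control rates with the effect measure named, is an optional courtesy to the reader.

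This conclusion rests on equal allocation and on reading the 23% as the intervention rate, which is the reading that reproduces 115 per group.

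### Hypothesis 2 concerns the number of non-urgent ED visits across literacy levels, but the sized primary is any ED use (yes/no) and no named analysis uses counts, non-urgent visits or literacy

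*Protocol*

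**What the plan says.** Section 2b sets the aim. Objective 2 is to "Assess how text messaging affects urgent and non-urgent health care utilization across caregivers with varying levels of health literacy", and Hypothesis 2 is "Receiving educational text messages reduces the number of non-urgent visits to the ED for caregivers across all levels of health literacy". The hypothesis therefore has three elements: a number of visits, visits that are non-urgent, and levels of health literacy.

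Section 3b provides for the data. At enrolment "caregivers will complete a brief demographic survey and be given a researcher-administered health literacy test", and at record review "The research team will type and count visits to the emergency department and Danis Pediatrics, as well as call volume".

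Section 3d fixes the analysis. "The primary outcome of 6-month ED use (no vs. yes) will be compared between study groups", by a chi-squared test. The sample size rests on the same variable, with this reason: "The study was powered on the latter variable because it is expected to yield the smallest intervention effect". The other analyses named are:

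- chi-squared tests for other categorical outcomes;
- logistic regression for dichotomous outcomes, with "covariates like patient age, race, gender, etc., included as control variables";
- an optional Cox model, for example for "time to first ED visit after study entry".

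The one stratification of the treatment effect that is named is by self-reported use of the texts.

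**The concern.** The primary contains none of the three elements of Hypothesis 2. A child with one urgent visit and a child with five non-urgent visits are both coded yes. Urgent visits, which the texts may not change, dilute the comparison, and a drop from several visits to one is not seen.

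The primary can therefore mislead in both directions. A null result could hide a real fall in non-urgent visits, and a positive one would not show which kind of visit fell. As the plan stands, either result could be reported as the answer to Hypothesis 2. The literacy part has no stated analysis.

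**Working it through.** **1. What the sample size rests on.** Inputs from section 3d: control rate 41%, intervention 20% to 25%, two-sided 5%, 80% power. The pooled two-proportion formula with continuity correction gives 84 per group for 20%, 116 for 23% (115.08 before rounding up) and 147 for 25%. The plan states 84, 115 and 147. Without the correction the results are 75, 105 and 135, which do not match. The sizing is thus a comparison of two any-ED proportions. No count, non-urgent rate or literacy stratum enters it.

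**2. Hypothesis against named analyses.**

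| Element of Hypothesis 2 | Collected (3b)? | Used in a named analysis (3d)? |
|---|---|---|
| Number of visits | Yes, counted | No; all named outcomes are yes/no, categorical or time to first event |
| Non-urgent | Visits are typed | Not named |
| Literacy levels | Yes, tested at enrolment | Not named |

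**3. Illustration of what the mismatch could cost.** The protocol gives no urgent share and no dispersion, so these are assumptions:

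- The clinic figures in section 1a (520 patients, 919 visits in half a year) and the 41% in 3d describe one population.
- Counts are negative binomial, with one dispersion parameter k for all visits and for non-urgent visits.
- Urgent visits are unchanged by the texts.
- The urgent share u is 20% to 50%.

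Fitting: N = 520/0.41 = 1268; mean = 919/1268 = 0.7246 visits per child; k = 0.8734 solves (1 + 0.7246/k)^(−k) = 0.59. Then P(any) = 1 − (1 + m/k)^(−k) for mean m.

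Power for proportions, n = 115 per group, with p̄ = (p1 + p2)/2:
Φ{[|p1 − p2| − 1.96√(2p̄(1 − p̄)/n)] / √([p1(1 − p1) + p2(1 − p2)]/n)}.

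Power for the count is a Wald test on the log rate ratio, with variance (1/m + 1/k)/n per arm.

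Worked case, u = 30%, non-urgent visits halved:

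- Any ED use: intervention mean 0.7246 × (0.30 + 0.70 × 0.5) = 0.471, so P(any) = 0.314 against 0.41, and power is 33%.
- Non-urgent count: means 0.507 and 0.254, SE = √(8.205/115) = 0.267, 0.693/0.267 = 2.595, and Φ(2.595 − 1.96) = 74%.

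Non-urgent visits halved:

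| Urgent share | Any ED use, control vs intervention | Power, any ED use | Power, any non-urgent visit | Power, non-urgent count |
|---|---|---|---|---|
| 20% | 0.41 vs 0.297 | 43% | 63% | 78% |
| 30% | 0.41 vs 0.314 | 33% | 61% | 74% |
| 40% | 0.41 vs 0.330 | 24% | 58% | 69% |
| 50% | 0.41 vs 0.345 | 17% | 54% | 63% |

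Most of the gap comes from including urgent visits; reducing the count to yes/no costs a further 9 to 14 points. Halving non-urgent visits cuts all visits by 0.5 × (1 − u), that is 40% to 25%. In this model the design's 41% to 23% needs a mean of 0.305, a 58% fall.

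Fall in non-urgent visits needed for 80% power:

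| Urgent share | Any ED use | Any non-urgent visit | Non-urgent count |
|---|---|---|---|
| 20% | 70% | 58% | 51% |
| 30% | 80% | 59% | 53% |
| 40% | 93% | 61% | 56% |
| 50% | not reachable (67% power with every non-urgent visit removed) | 63% | 59% |

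**4. Literacy.** Assume literacy splits each arm in half, with an 18-point effect (41% to 23%) in one half and none in the other. The interaction SE is √[(0.419 + 0.484)/57.5] = 0.125, and power is Φ(0.18/0.125 − 1.96), about 30%. An interaction cannot be a confirmatory test at this size.

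**The case against.** The strongest reply is that this is mostly an absence. Any ED use is legitimate under Objective 2, which covers urgent and non-urgent use, and a count model or coding rule could sit in a statistical analysis plan that is not shown. The lists in 3d are also open: other categorical outcomes could include any non-urgent visit, and the covariates could include literacy. That much stands. But a categorical outcome is still not a number of visits, and a control variable does not show the effect at each literacy level. A later plan could add analyses without removing the conflict between the hypothesis and the primary, which the protocol itself fixes. The smallest-effect rationale justifies the sample size; it does not supply a test of Hypothesis 2.

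The literacy phrase could mean only that the effect is general. That is a fair reading, and a reason to keep the literacy analysis descriptive.

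The illustration is open to challenge. Nothing says the 2014 visit figures and the 41% share a denominator, and they describe patients under 13 months rather than newborns followed from enrolment. The cut matters too: section 1a cites reductions of up to 80%, and at that cut power for any ED use is 93/80/62/43% across the four urgent shares, while both non-urgent tests reach about 98% or more. On the plan's continuity-corrected basis, the any-ED figures for halving are lower still, 38/28/20/14%. The figures are therefore indicative only.

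Finally, section 3b does not define how visits are typed, so urgency may need some further abstraction from the same records.

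**Conclusion.** The concern holds. Hypothesis 2 and the sized primary describe different outcomes, and no analysis named in the protocol tests the hypothesis as worded. Confidence in the mismatch is high, since it rests on the text alone.

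Its cost in power is uncertain and depends on the urgent share, the size of the fall and the fitted dispersion. If non-urgent visits are halved, the illustration gives the primary 17% to 43% power against 63% to 78% for the count. If they fall by 80% and few visits are urgent, the primary does well. The trial can run as designed, but this should be corrected before records are reviewed.

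**What to change.** 1. Keep 6-month any ED use with the chi-squared test as the sized primary. State that its conclusion and the 80% power apply to that outcome only.
2. Name the number of non-urgent ED visits as the key secondary that tests Hypothesis 2, over the same 6-month window. State where the window starts. Study entry, already the origin for time to first ED visit, would serve: with enrolment at 0 to 2 months the window ends by 2 + 6 = 8 months of age, inside the one-year record review.
3. Analyse it by negative binomial regression with Group, baseline health literacy, other baseline covariates and a log follow-up offset (which matters only where follow-up is incomplete).
4. Report the Group effect by literacy level with a Group-by-literacy term, labelled descriptive.
5. Classify each visit as urgent or non-urgent by a rule fixed before data review and applied blind to arm.

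The cost is protocol wording, one extra model and a written rule. The record review and the literacy test are already planned, and the sample size and the cap of 260 stay. There are downsides: urgency coding involves judgement and perhaps some extra abstraction, and the key secondary has no guaranteed power. The change does not raise the power of the primary; it only stops the primary standing in for Hypothesis 2.
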